3.1 Analysis sets

The following analysis data sets will be used in the analyses:

Full analysis set (FAS): The FAS will include all subjects who have received at least one dose of the study drug. The FAS will be the primary set for efficacy analyses.

Safety set (SS): The SS will include all subjects who have received at least one dose of the study treatment and had at least one post-baseline safety assessment. A subjects who has received a dose of study treatment and who has no post-treatment safety data of any kind (i.e., no AE assessment, no vitals, no ECG, no cardiac imaging, no ECOG performance status, and no laboratory assessment) will be excluded from the SS. Note that the statement ‘no adverse event’ is considered as an assessment of AE.

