8.1 Adverse events

8.1.1 Definitions and reporting

An adverse event (AE) is defined as the appearance of (or worsening of any pre-existing) undesirable sign(s), symptom(s), or medical condition(s) that occur after patient's signed informed consent has been obtained.

For patients who sign the ICF, all AEs will be captured in the AE eCRF from time of signature through 30 days after permanent study treatment discontinuation. For patients who fail the screening, only SAEs will be captured in the AE eCRF page.

Abnormal laboratory values or test results occurring after informed consent constitute adverse events only if they induce clinical signs or symptoms, are considered clinically significant, require therapy (e.g., hematologic abnormality that requires transfusion or hematological stem cell support), or require changes in study medication(s).

Adverse events that begin or worsen after informed consent should be recorded in the Adverse Events eCRF. Conditions that were already present at the time of informed consent should be recorded in the Medical History eCRF. Adverse event monitoring should be continued for at least 30 days following the last dose of study treatment. Adverse events (including lab abnormalities that constitute AEs) should be described using a diagnosis whenever possible, rather than individual underlying signs and symptoms. When a clear diagnosis cannot be identified, each sign or symptom should be reported as a separate Adverse Event.

Adverse events will be assessed according to the Common Terminology Criteria for Adverse Events (CTCAE) version 4.03. If CTCAE grading does not exist for an adverse event, the severity of mild, moderate, severe, and life-threatening, corresponding to Grades 1-4, will be used. CTCAE Grade 5 (death) will not be used in this study; rather, information about deaths will be collected through a Death form.

The occurrence of adverse events should be sought by non-directive questioning of the patient (subject) during the screening process after signing informed consent and at each visit during the study. Adverse events also may be detected when they are volunteered by the patient (subject) during the screening process or between visits, or through physical examination, laboratory test, or other assessments. As far as possible, each adverse event should be evaluated to determine:

1. The severity grade (CTCAE Grade 1-4)
2. Its duration (Start and end dates)

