3. Its relationship to the study treatment (Reasonable possibility that AE is related: No, Yes)
4. Action taken with respect to study or investigational treatment (none, dose adjusted, temporarily interrupted, permanently discontinued, unknown, not applicable)
5. Whether medication or therapy taken (no concomitant medication/non-drug therapy, concomitant medication/non-drug therapy)
6. Outcome (not recovered/not resolved, recovered/resolved, recovering/resolving, recovered/resolved with sequelae, fatal, unknown)
7. Whether it is serious, where a serious adverse event (SAE) is defined as in [Section 8.2.1](#).

All adverse events should be treated appropriately. If a concomitant medication or non-drug therapy is given, this action should be recorded on the Adverse Event eCRF.

Once an adverse event is detected, it should be followed until its resolution or until it is judged to be permanent, and assessment should be made at each visit (or more frequently, if necessary) of any changes in severity, the suspected relationship to the study treatment, the interventions required to treat it, and the outcome.

Progression of malignancy (including fatal outcomes), if documented by use of appropriate method (as per RECIST 1.1 criteria for solid tumors), should not be reported as a serious adverse event or adverse event.

Adverse events separate from the progression of malignancy (example, deep vein thrombosis at the time of progression or hemoptysis concurrent with finding of disease progression) will be reported as per usual guidelines used for such events with proper attribution regarding relatedness to the drug.

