10.5.3.1 Analysis set and grouping for the analyses

10.5.3.1.1 Adverse events (AEs)

All adverse events recorded during the study will be summarized. The incidence of treatment-emergent adverse events (new or worsening from baseline) will be summarized by presenting the number and percentage of patients by system organ class and/or preferred term, maximum severity (based on CTCAE v4.03), type of adverse event, and relationship to the study treatment. In addition, adverse events of related nature may be analyzed by categories regrouping the relevant preferred terms, as appropriate. Adverse events that occurred on the same subject in the same system organ class and/or preferred term will be counted only once for the one with the highest severity.

Deaths reportable as SAEs and non-fatal serious adverse events will be listed by patient and tabulated by type of adverse event and patient group.

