7.1 Adverse events

Adverse events data will be collected at each visit. They will be assessed according to the most current version of the Common Toxicity Criteria for Adverse Events (CTCAE). If CTCAE grading does not exist for an adverse event, the severity of mild, moderate, severe, and life-threatening, or grades 1-4 were used. CTCAE grade 5 (death) was not used in this study; rather, this information was collected in the End of Treatment/Study or Survival Information CRF page.

All AEs will be coded by Preferred Term (PT) and associated primary System Organ Class (SOC) using MedDRA (Medical Dictionary for Regulatory Activities, version 16.1 or above). The CRF collects the verbatim term for MedDRA coding.

Summaries of AE will be based on treatment emergent adverse events (TEAEs), which is defined as all new or worsening events collected from first study treatment date to last treatment date + 30. Novartis standard partial date imputation methods will be used for imputation of partial AE onset/resolution dates.

Analysis of Adverse Events

In general, the subject incidence of TEAEs will be summarized for all tables, unless otherwise noted, by SOC and PT. TEAEs will be shown in alphabetical order for SOCs and in decreasing frequencies for PTs within each SOC. Subject frequencies and percentages will be presented.

All summaries will be based on subject counts (i.e., the number and percentage of subjects who satisfy the criteria), and will depict all AEs and all grade 3/4 AEs at minimum. Each subject will be counted at most once per category. For subjects with multiple grades for the same event, only the worst grade will be counted.

The following summary tables will be provided for the SS:

- Summary of TEAEs by SOC, PT, and maximum severity
- Summary of serious TEAEs by SOC and PT
- Summary of the most common TEAEs (10% or more of subjects) by PT and decreasing frequency
- Summary of suspected TEAEs by SOC and PT
- Summary of TEAEs associated with permanent discontinuation of study drug
- Summary of TEAEs associated with dosage adjusted/temporarily interrupted of study drug
- Summary of adverse events of special interest (see details below in Section 7.1.1)

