7.2 Deaths

A subject listing of deaths with recorded principal cause of death (if available) will be provided.

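### A dosed patient who dies before any post-dose safety record falls outside the Safety Set, and no SAP table identifies fatal adverse events or counts deaths to 30 days after the last dose

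*SAP*

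**What the plan says.** **Safety Set.** Protocol 10.1.2 and SAP 3.1 give the same two-part rule: at least one dose, and the patient "had at least one post-baseline safety assessment". SAP 3.1 then spells out who is excluded: a dosed subject "who has no post-treatment safety data of any kind (i.e., no AE assessment, no vitals, no ECG, no cardiac imaging, no ECOG performance status", with laboratory assessment closing the list. It adds that a statement of no adverse event "is considered as an assessment of AE". The Full Analysis Set needs only a dose.

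**How deaths are recorded.** Protocol 8.1.1 states: "CTCAE Grade 5 (death) will not be used in this study; rather, information about deaths will be collected through a Death form". SAP 7.1 agrees that "CTCAE grade 5 (death) was not used in this study" and places the information on the end-of-treatment/study or survival page. Protocol 8.1.1 also keeps some deaths out of adverse event reporting altogether: "Progression of malignancy (including fatal outcomes), if documented by use of appropriate method" is to be reported neither as an adverse event nor as an SAE.

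**How deaths are reported.** Protocol 10.5.3.1.1: "Deaths reportable as SAEs and non-fatal serious adverse events will be listed by patient and tabulated by type of adverse event and patient group". SAP 7.2: "A subject listing of deaths with recorded principal cause of death (if available) will be provided". SAP 7.1 plans a table of serious treatment-emergent events by system organ class and preferred term, and requires summaries to show at least all events and grade 3/4 events. SAP 2.1 pools all subjects for safety but does not mention the tabulation of deaths.

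**The concern.** There are two separate weaknesses.

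First, entry to the Safety Set depends on something that happens after dosing, and a very early death is one way to fail the condition. The exclusion is therefore related to outcome, although it reaches few patients.

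Second, a reader of the safety tables cannot tell which events were fatal. Severity stops at grade 4 and the serious-event table has no fatal split, so a fatal event looks like any other serious event. Nor does a table give the number of patients who died between the first dose and 30 days after the last, which is the SAP's own window for treatment-emergent events. In a single-arm study, where toxicity has no concurrent comparator, that is a basic figure that readers will want.

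**Working it through.** The plan states no figure on this point, so there is none to reproduce. The check is a comparison of rules, followed by a calculation of scale.

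**Step 1: who can leave the Safety Set.**

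| Situation after the first dose | Record created | In Safety Set? |
|---|---|---|
| Fatal adverse event | A fatal event is an SAE (protocol 8.2.1), so there is an adverse event record | Yes |
| Any post-dose laboratory, vital-sign, ECG, imaging or ECOG result | Yes | Yes |
| Entry of no adverse event, without a visit | Counts as an assessment (SAP 3.1) | Yes |
| Death from documented progression before any post-dose result, with no adverse event entry | Death information only | No |

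The first scheduled post-dose assessment is haematology and biochemistry on Cycle 1 Day 8, with a window of 4 days either side (protocol Table 7-1 and 7.2.2.6). The exposed period is therefore about the first week or so. The documents do not say how many patients would fall in the last row.

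**Step 2: the effect of one such patient.** With safety pooled (SAP 2.1), the proportion who died is 1/N if all dosed patients count, and 0/(N − 1) under the present rule.

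- N = 70: 1/70 = 1.43% against 0/69 = 0%.
- N = 120: 1/120 = 0.83% against 0/119 = 0%.

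The range 70 to 120 is from protocol 5.1. SAP section 2 gives about 70 to 90; 1/90 = 1.11%.

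**Step 3: where a death would appear.**

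| SAP output | What it shows | What it leaves out |
|---|---|---|
| Serious events by class and term (7.1) | Includes fatal SAEs | Which ones were fatal |
| Events by maximum severity (7.1) | Grades up to 4 | Fatal outcome |
| Disposition (3.2) | Death as the reason for stopping treatment | Deaths within 30 days after stopping for another reason |
| Listing of deaths (7.2) | Each death, with cause if available | Any count or percentage |
| Overall survival (6.4) | Deaths at any time | The 30-day window and the cause |

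No row gives a count of fatal events or of deaths to last dose plus 30 days. The data are collected: fatal is one of the adverse event outcomes in protocol 8.1.1, and SAP 6.3 already uses death within 30 days of the last dose for progression-free survival.

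**Step 4: are there likely to be deaths to report?** Protocol 1.2.1.2.1 reports 6 deaths on study among 207 dosed phase I patients: 6/207 = 2.9%. Assume that this share carries over. Expected deaths = N × 6/207, and the chance of at least one = 1 − (1 − 6/207)^N.

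| N | Expected | Chance of at least one |
|---|---|---|
| 70 | 2.0 | 87% |
| 90 | 2.6 | 93% |
| 120 | 3.5 | 97% |

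The six are one category of discontinuation reason (135 + 28 + 6 + 15 + 1 + 1 = 186), so any death shortly after stopping for another reason is not among them.

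**The case against.** The best defence is that deaths remain visible and that the exclusion hardly bites. Much of this stands.

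- A reader might infer that any dosed patient without a later safety visit is removed. The documents do not say so. There must be no safety data of any kind, an entry of no adverse event is enough, and protocol 7.1.4.1 requires 30 days of safety contact even with patients who refuse a final visit. Entry also requires ECOG 0 or 1 and a life expectancy of at least 16 weeks (protocol 5.2).
- A reader might infer that the deaths protocol 10.5.3.1.1 promises to tabulate are those lost from the set. They are not. A death reportable as an SAE creates an adverse event record, so that patient stays in the set and in the serious-event table.
- The serious-event table can be read as meeting the protocol sentence, which puts fatal and non-fatal serious events together. SAP section 1 also says that the remaining data are analysed according to protocol section 10, and SAP 2.1 declares the loss of the patient-group split. This weakens a charge that the tabulation was dropped outright. It does not supply a table in which fatal events can be recognised, and SAP 7.2 speaks only of a listing.
- The Safety Set rule is the protocol's own, so it is not a SAP deviation.
- In a study of this size, each death can be traced in the listings. That is true, but a listing gives the reader no count or percentage.

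**Conclusion.** The point holds in a limited form. The Safety Set wording can exclude a dosed patient who dies before any post-dose safety record. That should be rare, and each case moves a pooled death proportion by about 0.8 to 1.4 percentage points, for 120 down to 70 patients. The reporting gap is the more practical matter: no SAP table separates fatal from non-fatal treatment-emergent events or counts deaths to last dose plus 30 days, and SAP 2.1 does not explain why deaths are only listed.

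Two readings of size should be avoided. The phase I share of 6/207 shows only that some on-treatment deaths are likely (about 2 to 3.5 in 70 to 120 patients, if the share carries over), not how many patients would leave the Safety Set. A reader might also reckon one lost patient as 10 percentage points in a cohort of 10, but SAP 2.1 pools safety, so no such cohort table is planned.

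This is an inexpensive improvement and does not threaten the study's conclusions.

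**What to change.** 1. Define the Safety Set in protocol 10.1.2 and SAP 3.1 as all patients who received at least one dose. It then equals the Full Analysis Set, and no dosed patient can leave the denominator.
2. Add to SAP 7.1 one table of treatment-emergent events with fatal outcome, by system organ class and preferred term, taken from the adverse event outcome field. If the sponsor prefers the listing alone, state that in SAP 2.1 as a change from protocol 10.5.3.1.1.
3. As a recommendation beyond what the protocol requires, add to SAP 7.2 a count of deaths from first dose to last dose plus 30 days by cause: progression, adverse event, other, and not recorded. The last row is needed because SAP 7.2 gives cause only where available.

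The cost is a few lines of SAP text and two short tables from data already collected. The protocol line needs a written amendment (protocol 12.1) and can go with the next one.

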3.2 Subject disposition

The number and percentage of subjects who completed study treatment or prematurely discontinued from the study treatment will be summarized with reasons for premature discontinuation. The reasons for study treatment discontinuation are as follows:

1. Adverse events
2. Lost to follow-up
3. Death
4. Disease progression
 - a. Radiological assessment
 - b. Clinical assessment
5. Protocol deviation
6. Non-compliance with study treatment
7. Pregnancy
8. Physician’s decision
9. Subject/guardian decision
10. Study terminated by sponsor

In addition, the number and percentage of subjects who consent to be followed for survival will be presented.

For subjects who were screened but did not take the study treatment, a listing with reasons for screen failure will be provided. The reasons collected for screen failure are as follows:

1. Unacceptable past medical history/concomitant diagnosis
2. Intercurrent medical event
3. Unacceptable laboratory value(s)
4. Unacceptable test procedure result(s)
5. Did not meet diagnostic/severity criteria
6. Unacceptable use of excluded medications/therapies
7. Subject withdrew consent
8. Unknown
9. Other

In addition, a listing of subjects’ deviations/violations during the study will be provided.

3.3 Study Treatment and other concomitant medications

Subjects receive BGJ398 at 125 mg once daily, 3 weeks on 1 week off. A complete treatment cycle is 28 days. There is no break between dosing cycles. For subjects who are unable to tolerate the protocol-specified dosing schedule, dose adjustments are permitted in order to allow these subjects to continue study treatment. Protocol section 6.3 provides the details.

In general, concomitant medications and therapies deemed necessary for the care of the subject are permitted (see Protocol Section 6.4.1 and 6.4.2), except as specifically prohibited (see Protocol Section 6.4.3). All medications, procedures and significant non-drug therapies (including physical therapy and blood transfusions) administered within 30 days prior to the administration of BGJ398 and through 30 days after the last dose of study treatment will be recorded in the corresponding CRF page.

Detailed summaries of study treatment and other concomitant medications are described in Section 5 below.

4 Patient demographics and other baseline characteristics

Demographic data, medical history, disease characteristics and other baseline characteristics are collected at the screening visit.

In general, the baseline value will be considered as the last measurement observed prior to the first dose of study treatment, and includes assessments taken on the date of the first dose of study treatment.

Unless specified otherwise, for continuous data, the mean, standard deviation, median, 25th and 75th percentiles, minimum, and maximum will be presented. For categorical data, frequencies and percentages will be presented.

Demographic characteristics

Demographic variables include:

- Age (years), age group (<65, ≥65-<75, ≥75 years)
- Sex (Male, Female – able to bear children, premenarche, post menopausal, sterile or child bearing age)
- Race (Caucasian, Black, Asian, Native American, Pacific Islander, Other)

Medical history

Number and percentage of subjects with relevant and/or current medical history/conditions will be summarized by categories of conditions. For ongoing conditions, grade of condition (i.e., 1-4) will also be summarized. Medical history/current medical conditions will be coded using Medical Dictionary for Regulatory Activities (MedDRA). The MedDRA version used for reporting the study will be specified as a footnote in the tables/listings.

Disease characteristics

Disease characteristics variables include:

- Gene mutations as detected by local and central labs in pre-defined per-protocol mutation categories
- Primary tumor type (**Sponsor adjudicated**)
Note: The tumor type adjudication is made based on the combination of the primary site of tumor with the tumor histology/cytology as collected in the CRFs.
- Time (in months) from initial diagnosis to the first dose of BGJ398
- Time (in months) from date of most recent recurrence/relapse to the first dose of BGJ398
- Presence of B symptoms (for lymphoma subjects only)
- Stage at initial diagnosis
- Age of biopsy samples (in months) calculated from date of biopsy sample date to the first dose of BGJ398

Other baseline assessments

- Vital signs (height, weight, body temperature, respiratory rate, sitting pulse, sitting systolic/diastolic blood pressures [SBP/DBP])
- 12 lead ECG (QTcF, heart rate, PR duration, QT duration, QRS duration)
- Cardiac imaging (LVEF)
- ECOG performance status
- Prior lines of antineoplastic medication therapy
- Prior antineoplastic radiotherapy (yes/no)
- Prior antineoplastic surgery (yes/no)

5 Study treatment exposure and other medications

5.1 Study treatment

Duration of BGJ398 treatment (in months) and actual total dose (sum of daily BGJ398 treatment) will be summarized with mean, standard deviation, median, 25th percentile, 75th percentile, minimum and maximum. Duration of the treatment is defined as the last dose date of BGJ398 minus the first dose date of BGJ398 + 1. The number and percentage of subjects with BGJ exposure for the following categories will be presented as well: day 1 – day 61 (\leq 2 month), day 62 – day 122 ($>$ 2 months - \leq 4 months), day 123 – day 183 ($>$ 4 months - \leq 6 months), day 184 – day 244 ($>$ 6 months - \leq 8 months), day 245 – day 365 ($>$ 8 months - \leq 12 months), and \geq day 366 ($>$ 12 months).

Actual dose intensity and relative dose intensity of BGJ398 will be summarized. Dose intensity is defined as the total dose of BGJ398 (mg) divided by duration of BGJ398 (in days). Relative dose intensity (in percent) is the actual dose intensity divided by planned dose intensity (i.e., 125 mg/day), and expressed in percent.

In addition, the number and percentage of subjects who had a dose change will be summarized with reasons for the change (as per protocol: AE, dosing error, lab test abnormality, scheduling conflict, or dispensing error).

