6.1.1 Dosing regimen

BGJ398 will be dosed on a flat scale of 125 mg (e.g., 1 x 100 mg and 1 x 25 mg capsules) once daily for the first 21 days of the 28-day cycle (3 weeks on, 1 week off in a cycle). A complete treatment cycle is defined as 28 days (refer to [Table 6-1](#)).

The patient must continue to meet all eligibility criteria on C1D1, as they did during the screening period. Refer to [Section 7.1](#) for more details.

Table 6-1 Dose and treatment schedule

Study treatment	Pharmaceutical form and route of administration	Dose	Frequency and/or Regimen
BGJ398	Capsule(s) for oral use	125 mg (administered as one 100 mg capsule and one 25 mg capsule)	Daily (3 weeks on, 1 week off schedule in 28-day cycles)

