7.1.2 Treatment period

Patients will be treated with BGJ398 (125 mg, orally, once-a-day,) until disease progression, unacceptable toxicity, death or discontinuation from the study treatment due to any other reason.

For details of safety and efficacy assessments, refer to [Table 7-1](#) and [Section 7.2](#).

- Visits and associated assessments that occur \pm 4 days from the scheduled date (except for cycle 1 Day1 where no visit window is allowed) will not constitute protocol deviations.
- The cycle length is 28 days. Day 1 of subsequent cycles will be calculated from cycle 1, day 1.
- Disease Assessments (per RECIST or appropriate hematological response criteria) must be performed every 8 weeks (\pm 4 days) after first dose of study drug (Day 1 of every odd cycle), until disease progression or end of treatment, whichever occurs first. Upon implementation of this amendment, the frequency of disease assessment will be reduced and evaluations should be every 16 weeks after the first 16 weeks on treatment.
- Laboratory assessments performed as part of the screening evaluations and within 4 days of the first dose of study treatment, are not required to be repeated on the first dosing day.
- [REDACTED]
- [REDACTED]
- For ongoing patients with TIO diagnosis FGF23 plasma assessment and 1-25-dihydroxy vitamin D will be collected, refer to [Table 7-1](#) and [Section 7.2.2.6.7](#).

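### SAP 5.1 sets calendar-day dose intensity against 125 mg per dosing day, so a fully compliant patient treated beyond cycle 1 scores about 75% to 85.7% instead of 100%

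*SAP*

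**What the plan says.** SAP 5.1 builds the measure in three steps.

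- Duration: "Duration of the treatment is defined as the last dose date of BGJ398 minus the first dose date of BGJ398 + 1". This is a calendar-day count.
- Dose intensity: "Dose intensity is defined as the total dose of BGJ398 (mg) divided by duration of BGJ398 (in days").
- Relative dose intensity: "Relative dose intensity (in percent) is the actual dose intensity divided by planned dose intensity (i.e., 125 mg/day").

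The schedule is given in SAP 3.3: "Subjects receive BGJ398 at 125 mg once daily, 3 weeks on 1 week off", with "A complete treatment cycle is 28 days" and "There is no break between dosing cycles". Protocol 6.1.1 agrees that BGJ398 is taken "once daily for the first 21 days of the 28-day cycle (3 weeks on, 1 week off in a cycle"). Protocol 10.3.1 asks for dose intensity to be summarised but gives no formula and no planned value.

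**The concern.** The ratio mixes two bases. Actual dose intensity is spread over all calendar days between first and last dose, off weeks included. The planned value assumes 125 mg on each of those same days, which this schedule never intends once an off week has passed. Each planned off week inside the interval therefore counts as missed treatment.

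The size of the artefact varies. It is absent for patients who stop in cycle 1, appears abruptly at the start of cycle 2, and then depends on time on treatment and on the cycle day of the last dose. A mean or median of the measure would partly reflect how long patients stayed on treatment. Taken alone it could not separate a real dose reduction from planned rest, and it can put a compliant patient below one who received less than planned.

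**Working it through.** **Inputs.** 125 mg per dosing day, 21 dosing days per 28-day cycle, no gap between cycles (SAP 3.3, Protocol 6.1.1); duration = last dose date − first dose date + 1, and planned intensity 125 mg/day (SAP 5.1).

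**The plan's figure.** Per dosing day: 125 × 21 / 21 = 125 mg/day, which matches. Per calendar day over a full cycle: 125 × 21 / 28 = 93.75 mg/day, which does not. So 125 mg/day is a per-dosing-day value, while the duration it is paired with counts calendar days.

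**Score of a fully compliant patient.** With the last dose on dosing day j (1 to 21) of cycle k:

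- total dose = 125 × [21(k − 1) + j] mg
- duration = 28(k − 1) + j days
- SAP score = [21(k − 1) + j] / [28(k − 1) + j]

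| Day of last dose | Cycle, dosing day | Doses / calendar days | SAP score |
|---|---|---|---|
| 21 | 1, 21 | 21 / 21 | 100.0% |
| 29 | 2, 1 | 22 / 29 | 75.9% |
| 49 | 2, 21 | 42 / 49 | 85.7% |
| 57 | 3, 1 | 43 / 57 | 75.4% |
| 77 | 3, 21 | 63 / 77 | 81.8% |
| 105 | 4, 21 | 84 / 105 | 80.0% |
| 113 | 5, 1 | 85 / 113 | 75.2% |
| 329 | 12, 21 | 252 / 329 | 76.6% |

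Every row should read 100%. From day 29 on, the maximum is 85.7% (day 49). The lower limit is 21/28 = 75%, approached from above and never reached.

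**Comparison with real under-dosing.**

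- 100 mg on each of the 21 days of one cycle: 2100 / 21 / 125 = 80.0%. A patient who missed nothing through the dosing days of cycle 4 gets the same score.
- 125 mg in cycle 1 and 100 mg in cycle 2, last dose day 49: total 21 × 125 + 21 × 100 = 4725 mg. Share of planned dose: 4725 / (42 × 125) = 90.0%. SAP score: 4725 / 49 / 125 = 77.1%. A patient who missed nothing and took the last dose on day 29 scores lower, at 75.9%.
- 17 of 21 doses in cycle 1, last dose on day 21: 17 / 21 = 81.0%, above the fully compliant four-cycle patient's 80.0%.

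**The obvious repair, tested.** Keep the SAP duration and replace 125 by 93.75 mg/day. A compliant patient then scores 125 / 93.75 = 133.3% with a last dose in cycle 1, and (5250 / 49) / 93.75 = 114.3% at day 49. The error changes sign because the interval stops at the last dose and leaves out the final off week.

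**The case against.** The strongest reply is that little depends on this. Dose intensity is not an endpoint, and no hypothesis, stopping rule or analysis set uses it. Duration and total dose are summarised beside it. Dose changes are tabulated with reasons (SAP 5.1), and adverse events leading to dose adjustment or interruption have their own table (SAP 7.1). That stands: real dose changes will be visible elsewhere, and the confusion is confined to the relative measure. Those tables do not, however, show how much of the planned dose was lost, which is what relative dose intensity is for.

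A second reply is that the duration used for dose intensity might mean dosing days, in which case 125 mg/day would be right. The only definition of duration in the section is by first and last dose dates, so this is the weaker reading; if it was intended, the text still has to say so.

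A third is that days 29, 57 and 113 are the low points of their cycles, and that 85.7% occurs on one day only. This is fair: 75% to 85.7% is a pair of bounds, not a typical spread. But the high points after cycle 1 are wrong too, and the comparison of 81.0% with 80.0% uses one of them.

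Nor is this an unlisted departure from the protocol. Protocol 10.3.1 gives no formula, so SAP 2.1 had no change to record.

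**Conclusion.** The concern holds. Followed as written, SAP 5.1 gives a wrong relative dose intensity for every fully compliant patient whose last dose falls after cycle 1: too low by between 14.3 percentage points (100 − 85.7, at day 49) and just under 25. Patients whose last dose falls in cycle 1 are scored correctly. The figures assume 28-day cycles with no delay and every scheduled dose taken at 125 mg. Nothing elsewhere in the protocol or SAP corrects the formula. The consequence is a misleading descriptive exposure summary, which should be corrected before the exposure tables are produced; efficacy conclusions are not affected.

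**What to change.** Define relative dose intensity as

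actual cumulative dose / (125 mg × number of dosing days scheduled from first to last dose date under the 3-weeks-on, 1-week-off schedule) × 100.

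This gives 100% for a compliant patient at every duration. For the patient reduced to 100 mg in cycle 2 it gives the 90.0% actually received. Do not substitute 93.75 mg/day over the existing duration.

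The counting rule should be part of the definition. Protocol 7.1.2 supplies an anchor: "Day 1 of subsequent cycles will be calculated from cycle 1, day 1". The protocol glossary, however, allows a cycle to be extended for adverse events, and the SAP should say how scheduled days are counted then. The choice matters. Suppose cycle 2 starts 7 days late, so dosing begins on day 36, and the last dose is on day 42. Doses taken are 21 + 7 = 28. Counted from cycle 1 day 1, the scheduled days to day 42 are 21 + 14 = 35, giving 28 / 35 = 80.0%. If the schedule moves with the delayed cycle, 28 days are scheduled and the score is 100%.

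The cost is a sentence or two in the SAP and a revised derivation. Doses and dose changes are already recorded on the Dosage Administration Record eCRF (Protocol 6.1.1.1 and 6.3.1), so no new data are needed. The change concerns the summary formula only, not the dose or schedule.
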